The primary endpoint was RFS, and secondary endpoints included OS, distant metastasis-free survival (DMFS), freedom from relapse (FFR), and safety. The primary endpoint was met, with a 53% decrease in the relative risk of disease relapse or death observed with dabrafenib plus trametinib vs placebo (HR=0.47 [95% CI, 0.39-0.58]; P<0.001; median RFS, not reached in the dabrafenib+trametinib arm vs. 16.6 months in the placebo arm, respectively). RFS benefit with the combination treatment was observed across all patient subgroups analyzed, including BRAF mutation status, sex, age, disease stage, the presence of micro- or macrometastases and/or ulceration, and the number of nodal metastases. The OS results at the first interim analysis showed a favorable trend towards survival benefit in the dabrafenib + trametinib arm. Although the OS data was not mature, results favored the dabrafenib + trametinib arm, (HR, 0.57 [95% CI, 0.42-0.79]; P=0.0006); despite this low P value, the interim statistical significance threshold of $P=1.9 \times 10^{-5}$ was not reached. The combination treatment also resulted in DMFS and FFR improvements (49% and 53%, respectively) consistent with the RFS improvement observed (Long, 2017). In addition, the safety profile of the dabrafenib + trametinib combination in the COMBI-AD study was comparable to that observed in other approved indications, including unresectable/metastatic melanoma where it has been well characterized with consistent results

across two randomized Phase III studies. The AEs were manageable, and no new safety risks were identified.

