12.7 Interim analyses

One IA for futility of the primary endpoint is planned for the study when approximately the first 200 subjects dosed have been followed for 6 months (either completed 6 months of treatment or discontinued treatment earlier.) At the time of this IA, the futility of a secondary efficacy endpoint RFS will also be assessed. This analysis will allow assessing the impact of the adapted pyrexia AE-management algorithm on both the pyrexia event rate and the RFS rate at 6 months. The DMC will review the IA results and make a recommendation using the scenarios provided below. Any decision to stop or continue the pyrexia management algorithm will be made based on all data available at the IA cut-off taking the futility analysis into account.

From the COMBI-AD study that used the approved pyrexia management algorithm, the pyrexia event rate (composite rate of grade 3/4 pyrexia, hospitalization due to pyrexia, or permanent treatment discontinuation due to pyrexia) at 12 month observed for dabrafenib + trametinib (N=435) was: 20% with 95% CI (16%, 24%). Under the new pyrexia treatment algorithm, an observed primary endpoint rate of at least 20% may indicate lack of improvement of the new algorithm. Assessment of futility for primary endpoint will be based on the calculated Bayesian predictive probabilities of the event that observed pyrexia event rate will be 20% or more in the FAS, if the study is continued beyond the interim (i.e. till the primary analysis).

The pyrexia event rate is assumed to be binary and the number of subjects with pyrexia events is assumed to follow a binomial distribution. Suppose the prior belief regarding the probability of event rate (π) is that it has a beta distribution with parameters a_0 and b_0 . If there are x events out of n subjects, then the posterior distribution for π is beta with parameters $a_1 = a_0 + x$ and $b_1 = b_0 + n - x$. Now let Y represent the number of subjects with pyrexia events from m future observations, then the (posterior) predictive distribution of Y conditional on the observed data at the interim (x events out of n subjects) is a beta-binomial distribution described by

$$p(Y = y|x, n) = \binom{m}{y} \frac{B(a_0+x+y, b_0+n-x+m-y)}{B(a_0+x, b_0+n-x)}$$

where $B(a, b)$ is the beta function.

A diffuse (highly non-informative) prior distribution of the composite rate with a skeptical expectation of 20%, namely Beta (0.25, 1) is assumed.

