Under these assumptions, the DMC will be provided the predictive probability of observing pyrexia event rate of $\geq 20\%$, a criterion that may trigger consideration for stopping the study taking account of all available data and not just the pyrexia event rate data required for determination of futility.

Table 12-3 shows the predictive probabilities of observing pyrexia event rate $\geq 20\%$ ($n=200$) under different interim results. For illustration, with 200 subjects at IA, if the observed pyrexia event rate is 22%, the probability of observing the pyrexia event rate $\geq 20\%$ at primary analysis is $> 80\%$. The DMC might interpret this scenario as an outcome where stopping the study for futility may be a sensible option. If the observed pyrexia event rate is 18% at IA, the probability of observing the pyrexia event rate $\geq 20\%$ at primary analysis is $< 20\%$.

Table 12-3 Predictive probability of observing composite pyrexia event rate greater or equal 20% (n=200) in the safety set at primary analysis (600 subjects) under different interim results

Observed rate at IA (n=200)		Predictive probability of observing pyrexia event rate \geq 20% at primary analysis*
# of subjects with pyrexia events	%	
30	15	0.0135
32	16	0.0392
34	17	0.0943
36	18	0.1913
38	19	0.3318
40	20	0.5000
42	21	0.6673
44	22	0.8058
46	23	0.9015
48	24	0.9569
50	25	0.9838
52	26	0.9948
54	27	0.9986
56	28	0.9997
58	29	0.9999
60	30	1.0000

*prior distribution Beta (0.25, 1) is assumed.

At the time of this IA, the DMC will also be provided with interim results for the secondary endpoint RFS. Similar to the futility analysis for the primary endpoint, Bayesian predictive probabilities of the RFS rate will be provided.

From the COMBI-AD study, the Kaplan-Meier estimated RFS rate at 12 month for control group and treatment group were: 56% with 95% CI (51%, 61%) and 88% with 95% CI (85%, 91%), respectively. We consider the futility threshold of 12-month RFS rate of 61%, which is the upper bound 95% CI of control group, and calculate the predictive probability (PP) as follows:

$$PP = \text{Prob. [Observed 12 month RFS rate} \geq 61\% \mid x, n; x \text{ successes among } n \text{ subjects}]$$

The DMC will be provided the predictive probability of observing RFS of $\geq 61\%$, a criterion that may trigger consideration for stopping the study taking account of all available data and not just the RFS data required for determination of futility.

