Table 12-4 shows the predictive probabilities of observing RFS rate $\geq 61\%$ (n=200) under different interim results. For illustration, with 200 subjects at IA, if the observed RFS rate at 6-month is 65%, the probability of observing the RFS rate $\geq 61\%$ at the primary analysis at 12 months is $> 90\%$. If the observed RFS rate is 57%, the probability of observing the RFS rate $\geq 61\%$ at the primary analysis is $< 10\%$.

Table 12-4 Predictive probability of observing RFS rate greater or equal 61% (n=200) at the secondary analysis (600 subjects)

Observed rate at IA (n=200)	
-----------------------------	--

# of relapse free	%	Predictive probability of observing RFS rate \geq 61% at secondary analysis*
110	55	0.0163
112	56	0.0371
114	57	0.0760
116	58	0.1403
120	60	0.3550
122	61	0.4930
124	62	0.6321
128	64	0.8529
130	65	0.9201

*prior distribution Beta (0.37, 1) is assumed.

Subject enrollment will not be stopped for the IA. According to enrollment expectation, approximately 570 subjects are planned to be included in the study at the time of the IA cutoff.

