## 4 Study design

This is an open-label Phase IIIb study of dabrafenib in combination with trametinib in the adjuvant treatment of melanoma after complete resection. Patients with completely resected, histologically confirmed, BRAF V600E/K mutation-positive, high-risk [AJCC ed. 8 Stage IIIA (lymph node metastasis >1 mm), IIIB, IIIC or IIID] cutaneous melanoma will be screened for eligibility. The main purpose of the study is to assess whether an adapted AE-management algorithm for pyrexia (Fever (> 38 °C)), will reduce the incidence of Grade 3/4 pyrexia, hospitalization due to pyrexia and permanent treatment discontinuation due to pyrexia. The effectiveness of dabrafenib and trametinib therapy in this setting will also be assessed based on RFS and OS.

As per the protocol amendment version dated 09-May-2019, approximately 600 subjects were planned to be enrolled to receive dabrafenib (150 mg BID) and trametinib (2 mg once daily) combination therapy for 12 months. Due to global drug supply availability, the enrollment of patients was slower than anticipated, resulting in the final sample of 556 enrolled patients in the study by the end of anticipated recruitment period. The final sample size is reasonably close to the planned target.

At enrollment, subjects will be instructed on the pyrexia management algorithm (refer to protocol Section 6.5.1.1). Doses of study treatment may be modified and/or interrupted for management of toxicities associated with study treatment.

Three analyses are planned for this study.

- The interim analysis (IA) based on primary endpoint and secondary endpoint conducted when 203 subjects were dosed for 6 months (either completed 6 months of treatment or discontinued earlier). The data cut-off date was 16 August, 2019.
- The primary analysis is planned to be performed at 12 months after the last patient first visit (LPFV). The data cut-off is planned on 26th September, 2020.

[figure not shown]
- The final analysis will be performed at the end of the study defined as 24 months after LPFV.

At the time of IA, an independent data monitoring committee (IDMC) recommended to continue the trial without any changes.

This study consists of two Periods for Enrolled subjects:

- Treatment Period – subjects will receive up to 12 months of treatment (refer to the schedule as noted in protocol Table 8-1).

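### The interim RFS futility check sets a 6-month relapse-free count against a 12-month threshold, so Table 12-4 overstates the chance of reaching 61%

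*Protocol*

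**What the plan says.** Protocol 12.7 places the interim look at about 200 subjects followed for 6 months and says it will assess the algorithm's impact "on both the pyrexia event rate and the RFS rate at 6 months". For RFS the protocol states: "We consider the futility threshold of 12-month RFS rate of 61%, which is the upper bound 95% CI of control group". It defines the PP as the probability that the observed 12-month RFS rate is at least 61%, given x successes among n subjects. The DMC receives this PP as "a criterion that may trigger consideration for stopping the study taking account of all available data and not just the RFS data required" for determining futility.

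The illustration for Table 12-4 says that "if the observed RFS rate at 6-month is 65%, the probability of observing the RFS rate" ≥61% "at the primary analysis at 12 months is" above 90%, and that an observed 57% gives below 10%. The table assumes a Beta(0.37, 1) prior, 200 subjects at the interim and 600 at the end. Nothing in the section mentions events between months 6 and 12.

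SAP section 4 reports that the interim was "conducted when 203 subjects were dosed for 6 months" and that the committee "recommended to continue the trial without any changes". SAP 5.14 refers to a separate interim SAP for the methods.

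**The concern.** The input and the target are on different time scales. The count x is the number relapse-free at 6 months; the threshold and the predicted quantity belong to 12 months. RFS is time to recurrence or death, so a 12-month rate cannot exceed the 6-month rate in the same subjects. Using x unchanged assumes that nobody relapses or dies between months 6 and 12, and the future subjects are predicted on the same basis.

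The error is one-sided. A low PP would be lower still with the missing term, so it remains a sound warning. A high PP may be much too high. The check therefore leans towards continuing. Its purpose is to guard against lost efficacy under an algorithm that interrupts both drugs promptly and that, by the protocol's own account, had not been tested prospectively. Protocol 4.5 also names RFS futility, alongside the primary endpoint, as an occasion for a DMC recommendation on continuing, modifying or terminating the trial.

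**Working it through.** **Inputs.** From Protocol 12.7 and Table 12-4: n = 200 at the interim, N = 600 (so 400 further subjects), prior Beta(0.37, 1), threshold 61%, i.e. 0.61 × 600 = 366. The 12-month COMBI-AD rates are 56% (control) and 88% (treated). No 6-month RFS rate is given in either document.

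**Step 1: reproduce Table 12-4.** Enter x unchanged: Y ~ BetaBin(400, 0.37 + x, 1 + 200 − x) and PP = P(x + Y ≥ 366).

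| x | Table 12-4 | Recomputed |
|---|---|---|
| 110 | 0.0163 | 0.0164 |
| 112 | 0.0371 | 0.0374 |
| 114 | 0.0760 | 0.0765 |
| 116 | 0.1403 | 0.1409 |
| 120 | 0.3550 | 0.3561 |
| 122 | 0.4930 | 0.4942 |
| 124 | 0.6321 | 0.6332 |
| 128 | 0.8529 | 0.8536 |
| 130 | 0.9201 | 0.9205 |

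The largest difference is 0.0012. The table contains no month 6 to 12 term.

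**Step 2: add the missing term.** Let q be the probability of being relapse-free at 12 months given relapse-free at 6 months. Then PP(x, q) = P[Bin(x, q) + Bin(400, p₆q) ≥ 366], with p₆ ~ Beta(0.37 + x, 1 + 200 − x). Since q is not in the documents, it is varied.

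| q | 130/200 (65%) | 132/203 (65%), N = 556 |
|---|---|---|
| 1 | 0.92 | 0.92 |
| 0.99 | 0.88 | 0.88 |
| 0.95 | 0.60 | 0.59 |
| 0.938 | 0.49 | 0.47 |
| 0.90 | 0.17 | 0.15 |
| 0.88 | 0.07 | 0.06 |

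The last column uses the sizes reported in the SAP (target 340, since 0.61 × 556 = 339.2). The value 0.938 is √0.88, the constant-hazard figure implied by the treated arm.

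For 130/200 the PP crosses 0.90 at q = 0.9943, 0.50 at q = 0.939 and 0.10 at q = 0.888. The first is a loss of 0.57% of those relapse-free at month 6, or 0.57% × 0.65 ≈ 0.4% of all subjects.

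**Step 3: the count needed for PP ≥ 0.90.** It is 130 (65%) at q = 1, 136 (68%) at 0.95, 138 (69%) at 0.938, 144 (72%) at 0.90, 147 (73.5%) at 0.88, 155 (77.5%) at 0.832 and 172 (86%) at 0.748.

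**Step 4: the two ends.** At 114/200 (57%) the PP is 0.076 at q = 1, 0.050 at 0.99 and 0.006 at 0.95, so the below-10% sentence holds for any q. At 176/200 (88%) it is 0.982 at q = 0.748 and 1.000 for q ≥ 0.80.

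**Step 5: does the choice of q matter? (Illustration only.)** Take two assumed control-like curves with 56% RFS at 12 months, and flag a look when PP < 0.5. That cut-off is chosen here; the protocol sets none.

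- Constant hazard: 6-month RFS √0.56 = 0.748, so q = 0.748. Its median is 12 × ln 2 / −ln 0.56 ≈ 14.3 months, which does not fit the reported "16.6 months in the placebo arm".
- Weibull through 56% and 16.6 months: shape 0.550, 6-month RFS 0.673, q = 0.56/0.673 = 0.832.

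| Check | Flagged if x ≤ | Constant hazard | Weibull |
|---|---|---|---|
| As in Table 12-4 | 122 | 0.001% | 3.5% |
| q = 0.938 | 130 | 0.1% | 27% |
| q = 0.832 | 146 | 30% | 97% |
| q = 0.748 | 163 | 99% | 100% |

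Rounding of the two Weibull inputs alone moves the 3.5% between 1.3% and 8.3%. These rates show only that a corrected check depends heavily on which arm supplies q.

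**The case against.** The strongest reply is that little hangs on the sentence. The PP is advisory, no RFS cut-off is set, no rule says a high PP means continue, and the DMC sees all the data. The stopping-side example is correct. In COMBI-AD the treated arm had 88% RFS at 12 months, hence at least 88% at 6 months, and there the PP is near 1 with or without the correction. The interim is complete. All of this stands and limits the impact.

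A second reply is that 0.6% makes the error sound large: the printed value is only 0.92, so 0.90 is crossed almost at once, and a 2% loss still leaves 0.83. That is fair; a material change needs a loss of about 5% or more. But 0.938, the constant-hazard figure from the favourable treated arm, already takes the PP below one half.

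Third, the upper-bound statement presumes complete follow-up. Protocol RFS is a Kaplan-Meier quantity, and if subjects censored before month 6 are not counted as relapse-free, x/200 understates the 6-month rate. The table's own model ignores censoring too, so the statement holds within that model, and this qualification belongs with it.

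Finally, the interim SAP and DMC charter are not among the documents and may have handled this differently. The proposed action is conditional on that.

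**Conclusion.** The mismatch is real and follows from the protocol's own text and table. Under the table's model with complete follow-up, every PP in Table 12-4 is an upper bound for the probability that 12-month RFS reaches 61%, whatever q is. The above-90% statement at 65% requires almost no relapse or death between months 6 and 12. How far it is wrong depends on q, which is an assumption here: 0.60 at q = 0.95 and 0.17 at q = 0.90.

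The consequence is a safety check that is too lenient when RFS falls well towards the control level. The primary pyrexia conclusion and the descriptive RFS and OS estimates are unaffected. Whether the DMC used the table as printed is unknown. The point should be corrected.

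**What to change.** Put both sides on one time scale.

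- **Preferred:** compare the 6-month Kaplan-Meier RFS with the upper 95% limit of the COMBI-AD control rate at 6 months. This needs no q, but it does need that control estimate and its limit, which the documents do not give.
- **Alternative:** keep the 12-month threshold, add a month 6 to 12 term, name the arm that supplies it and show the PP over a range of q. A treated-arm q gives a much weaker check than a control-arm q.

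Then rebuild Table 12-4 and correct the above-90% sentence. As the interim is complete, unless the interim SAP already dealt with this, state in the SAP or CSR that the interim RFS PP assumed no relapse or death between months 6 and 12 and is, under that model with complete follow-up, an upper bound for 12-month RFS.

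The cost is one or two sentences, plus a recalculated table if the interim method is reported. No new trial data are needed.

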12.8 Sample size calculation

The sample size calculation is based on the primary variable. The sample size of 600 has been chosen so that the study operating characteristics comply with the requirement to have a high probability (e.g. > 95%) for futility at IA if the true 12-month pyrexia event rate is > 20%, e.g., when the true pyrexia event rate is 27%, the probability is 95.5% for futility.

Operating characteristics are described below (see [Table 12-5](#)). For illustration, if the true 12-months pyrexia event rate is 30%, then there is a high chance (99.6%) of futility at the time of the IA, and the probability to continue the study and conclude success is lower than 0.001.

If the true pyrexia event rate is 20%, then the probability of observing a pyrexia event rate < 20% (i.e., study success for primary analysis) is 43.4%. If the true pyrexia event rate is lower (for example 18%), then there is 83.9% probability of declaring study success for primary analysis.

Table 12-5 Operating Characteristics

True 6 -month event rate	Probability to stop the study at IA	Probability of success at primary analysis (i.e., not stop at the IA and observe event rate < 20% at primary analysis)
16%	0.016	0.980
17%	0.040	0.939
18%	0.086	0.839
19%	0.161	0.661
20%	0.265	0.434
21%	0.391	0.228
22%	0.528	0.094
25%	0.856	0.001
26%	0.917	<0.001
27%	0.955	<0.001
28%	0.978	<0.001

True 6 -month event rate	Probability to stop the study at IA	Probability of success at primary analysis (i.e., not stop at the IA and observe event rate < 20% at primary analysis)
30%	0.996	<0.001

Probabilities are calculated based on the exact binomial distribution.

13 Ethical considerations and administrative procedures

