## 6 Sample size calculation

As per the protocol amendent version dated 09-May-2019, approximately 600 subjects were planned to be enrolled to receive dabrafenib (150 mg BID) and trametinib (2 mg once daily) combination therapy for 12 months. Due to global drug supply availability, the enrollment of patients was slower than anticipated, resulting in the final sample of 556 enrolled patients in the study by the end of anticipated recruitment period. The final sample size is reasonably close to

the planned target. The impact of the reduced sample size for the interim analyses has been discussed in detail in the Interim SAP (dated 21-Nov-2019) and DMC charter (17-Jan-2020). See Section 2.8 and Appendix B respectively for details.

The sample size calculation was based on the primary variable. The protocol amendment dated provided justification for the planned sample size of 600. However the current sample size of 556 demonstrates that the study operating characteristics comply with the requirement to have a high probability (e.g. > 95%) for futility at IA if the true 12-month pyrexia event rate is > 20%, e.g., when the true pyrexia event rate is 27%, the probability is 95.5% for futility at interim analysis.

Detailed Operating characteristics are described below (see [Table 2-8](#)). For illustration, if the true 12-months pyrexia event rate is 30%, then there is a high chance (99.6%) of futility at the time of the interim, and the probability to continue the study and conclude success is lower than 0.001.

If the true pyrexia event rate is 20%, then the probability of observing a pyrexia event rate < 20% (i.e., study success for primary analysis) is 46.3%. If the true pyrexia event rate is lower (for example 18%), then there is 84.6% probability of declaring study success for primary analysis.

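### Tables 12-5 and 2-8 use one pyrexia rate for both the interim and the 12-month analysis, so the 95.5% and 99.6% futility probabilities quoted for a 12-month rate are upper bounds

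*Protocol*

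**What the plan says.** Protocol 12.7 places the futility look "when approximately the first 200 subjects dosed have been followed for 6 months", counting subjects who stopped treatment earlier. Protocol 12.4.1 assesses the composite endpoint over 12 months of treatment.

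Protocol 12.8 justifies the sample size of 600 by a futility probability above 95% when the true 12-month event rate exceeds 20%. It gives 27% (95.5%) as the example and adds that "if the true 12-months pyrexia event rate is 30%, then there is a high chance (99.6%) of futility". The supporting table heads its rate column "True 6 -month event rate".

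SAP 6 carries the argument over to 556 subjects. It states the requirement for the 12-month rate, says that "when the true pyrexia event rate is 27%, the probability is 95.5% for futility at interim analysis", and repeats the 30% example. Its Table 2-8 has the same 6-month header and the same stop column.

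On timing, protocol 4.1 says that pyrexia appears early in treatment and that most events fell within the 12-month window. Neither document says what share of first composite events had occurred by month 6.

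**The concern.** Header and text give different time frames for the same numbers, and both can be right only if the 6-month and 12-month rates are equal. The stop probability depends on the rate accrued when the interim data are cut. That rate cannot exceed the 12-month rate, and it is lower if any subject has a first composite event after the interim.

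These probabilities are the stated reason for choosing 600 subjects. The SAP uses them again to say that 556 subjects still comply. What is at stake is whether the design has the futility property claimed for it. Table 12-3 has the same feature: its 200 interim subjects contribute no further events before the primary analysis.

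**Working it through.** **Inputs.** Interim n = 200; prior Beta(0.25, 1); final N = 600 (protocol 12.7 and 12.8) or 556 (SAP 6); exact binomial probabilities (footnotes to Tables 12-5 and 2-8). Success in both tables means not stopping at the interim and then observing a rate below 20%.

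**Stopping boundary.** No boundary is stated for the stop column. At 22% of 200 = 44 events, Table 12-3 prints 0.8058, and protocol 12.7 comments on that row that "The DMC might interpret this scenario as an outcome where stopping the study for futility may be a sensible option". The beta-binomial predictive probability is 0.7414 at 43 events and 0.8058 at 44. A boundary of 44 fits the stop column; 43 and 45 do not (at 27% they give 0.969 and 0.937, against 0.955 printed).

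**Stop column reproduced.** P(X ≥ 44 | n = 200, p) is 0.2645 at p = 0.20, 0.9552 at 0.27 and 0.9955 at 0.30. The table prints 0.265, 0.955 and 0.996.

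**Success column reproduced.** The formula is Σ over x < 44 of P(X = x | 200, p) × P(Y < 120 − x | 400, p), with the same p in both factors. It gives 0.8389 at 18% and 0.4341 at 20% (printed 0.839 and 0.434). For N = 556, with 356 further subjects and a total below 112, it gives 0.8459 and 0.4633 (printed 0.846 and 0.463). One rate therefore serves both stages.

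**Stop probability when the two rates differ.** Let f be the share of subjects with a 12-month event who already have it at the interim. Then P(stop) = P(X ≥ 44 | 200, f × p12). The values of f are assumptions.

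| f | p12 = 27% | p12 = 30% |
|---|---|---|
| 1.00 | 95.5% | 99.6% |
| 0.99 | 94.7% | 99.4% |
| 0.95 | 89.8% | 98.5% |
| 0.90 | 79.9% | 95.5% |
| 0.80 | 47.3% | 77.0% |

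A 95% chance of stopping needs an interim rate of 0.2683. This means f ≥ 0.2683/0.27 = 0.994 for the 27% example and f ≥ 0.2683/0.30 = 0.894 for the 30% example.

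**Neither label fits both columns.**

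- If p is a 12-month rate, the stop column is an upper bound. The success column also shifts: at 20% and f = 0.90 it is 0.474, not 0.434.
- If p is a 6-month rate, the stop column is right for a strict 6-month look, but the success column is wrong. A 6-month rate of 18% with f = 0.90 means a 12-month rate of 0.18/0.90 = 20%, where success is 0.474, not the printed 0.839.

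**Table 12-3, row 36/200.** Draw the interim rate from Beta(0.25 + 36, 1 + 164). Let the 164 event-free subjects have later events with probability (p12 − p6)/(1 − p6), and apply p12 = p6/f to the next 400. The predictive probability of an observed rate of 20% or more is 0.19 at f = 1 (printed 0.1913), 0.33 at f = 0.95 and 0.50 at f = 0.90.

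**The case against.** The strongest reply is that the tables contain no arithmetic error and that f may be close to 1.

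- Protocol 12.7 says that "Any decision to stop or continue the pyrexia management algorithm will be made based on all data available at the IA cut-off", so six months is a minimum for subjects still on treatment. Amendment 1 reports 37 subjects started by 30 November 2018, and SAP 4 gives the interim cut-off as 16 August 2019. That is 259 days, or 259/28 = 9.25 study months, at the least for those subjects.
- Pyrexia is described as early (protocol 4.1).
- Subjects who stopped treatment before the interim are already counted and can add few later events, because the endpoint is on-treatment and early stoppers without pyrexia count as no event (SAP 5.5.1 and 5.5.3).
- The consequence is small. The futility rule is non-binding, and success is judged on the upper 95% confidence limit being below 20%. At a true 12-month rate of 20%, the chance of not stopping and ending with at most 100 of 600 events is 0.0214 at f = 1 and 0.0215 at f = 0.80.

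All of this stands, and it limits both size and severity. It does not remove the point: the documents give no value of f, and the 27% example has almost no room below f = 1.

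Two stronger readings are tempting, and the documents support neither. A reader might infer that the quoted probabilities are simply wrong 6-month figures. The success column shows that the tables are not purely 6-month calculations, and the 6-month header may itself be the slip. A reader might also infer that the data monitoring committee was given a predictive probability that was too low. Table 12-3 is illustrative, and the interim SAP and committee charter that governed the actual analysis are not available here.

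**Conclusion.** The point holds as one of labelling and of an unstated assumption. Both tables assume no first composite event between the interim and month 12. Header and text disagree on which rate is meant, and neither label fits both columns unless the two rates are equal.

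As statements about a 12-month rate, 95.5% and 99.6% are upper bounds. The direction is certain, but the size depends on f, which the documents do not give. The 27% example falls below the required 95% for f under about 0.994; the 30% example holds down to about 0.894. These figures rest on a boundary of 44 of 200, inferred because it reproduces the stop column, and on a single f for all subjects.

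The final success criterion and the conclusion do not change, and the interim has passed with a recommendation to continue. Severity is minor.

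**What to change.** Take f from the COMBI-AD times to first composite event, allowing for follow-up beyond 6 months at the interim cut-off. Recompute both the stop and the success columns of Tables 12-5 and 2-8 with separate, labelled interim and 12-month rates. Restate the futility figures in protocol 12.8 and SAP 6 to match. Recomputing the stop column alone would leave the success column inconsistent.

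If this is not done, correct the table headers. Then state in the text, and under Tables 12-3, 12-5 and 2-8, that the figures assume no first event after the interim, so that stop probabilities for a 12-month rate are upper bounds.

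The cost is a short recalculation and some wording. The stated futility probabilities may look less favourable; no trial decision changes.
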